4. POPULATIONS (ANALYSIS SETS) FOR ANALYSIS

4.1. Enrolled Participants

All participants who signed the informed consent form (ICF).

4.2. Full Analysis Set (FAS) (Week 0 – Week 24)

All participants who were randomized in the study. This analysis set will be used for efficacy analyses.

This SAP uses the following definitions:

- Natural Disaster includes the COVID-19 pandemic, specifically any site closures, site access restrictions, or lockdowns caused by the pandemic;
- Major Disruption includes the disruption in Ukraine and neighboring countries/territories beginning 24 February 2022.

Because there were no sites where **every** participant was unable to have data collected for the primary endpoint at Week 24 or missed ≥ 2 doses of study intervention prior to Week 24, all the sites will be included in the FAS.

In the analyses for this set, participants will be analyzed according to the randomized study intervention they were **assigned to**, regardless of the study intervention they actually received.

4.4. Per-Protocol Analysis Set (Week 0 – Week 24)

The Per-Protocol Analysis Set (PPAS) includes all participants in FAS who met all inclusion and exclusion criteria and had no major protocol deviations prior to Week 24 that could have impacted efficacy assessment per clinical judgement (Appendix 3). This analysis set will be used for the analyses of *selected* efficacy endpoints through Week 24. Participants to be excluded from this analysis will be identified prior to the Week-24 DBL and unblinding.

In the analyses for this set, participants will be analyzed according to the randomized study intervention they were **assigned to**, regardless of the study intervention they actually received.

4.5. Safety Analysis Set

All participants who received at least one (complete or partial) administration of any study intervention, ie, the treated population. This analysis set will be used for the safety analyses.

In the analyses for this set, participants will be analyzed per the study intervention they **actually received**, regardless of the study intervention they were randomized to.

4.6. Pharmacokinetics (PK) Analysis Set

All participants who received at least one complete administration of guselkumab and had at least one valid blood sample drawn for PK analysis.

4.7. Immunogenicity Analysis Set

All participants who received at least one (complete or partial) administration of guselkumab and who had at least 1 sample obtained after their first administration of guselkumab.

4.8. Pharmacodynamic (PD) Analysis Set

The PD analysis set will be defined in a separate analysis plan for biomarkers and PD analyses.

5. STATISTICAL ANALYSES

5.1. General Considerations

5.1.1. Visit Windows

In general, for safety and efficacy analyses, the nominal visit will be used for by-visit analyses. Exceptions exist for the following.

5.1.1.1. Visit Windows for Dosing and PK Analysis

All post-baseline visits from baseline through Week 24 will have a visit window of ± 4 days, and from Week 28 through Week 100 will have a visit window of ± 7 days. Week 112 or the final safety visit (12 weeks after the last dose in participants who discontinued study treatment) will have a visit window of ± 14 days. This information will be used to identify out-of-window dosing or visits.

For PK analyses, if a participant has an administration outside the visit window at a visit, the concentration data collected at and after that visit will be excluded from the by-visit data analyses.

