1.2. Study Design

[figure not shown]
This is a Phase 3b, multicenter, randomized, double-blind, placebo-controlled interventional study in participants with active PsA who had an inadequate response and/or intolerance to one prior anti-TNF.

A target of 450 participants will be randomly assigned in this study with 150 participants planned per intervention group: guselkumab q8w (n=150), guselkumab q4w (n=150), or placebo (n=150).

Stable doses of concomitant non-steroidal anti-inflammatory drugs (NSAIDs), oral corticosteroids (≤10 mg/day prednisone equivalent) and selected non-biologic DMARDs (methotrexate [MTX], sulfasalazine [SSZ], hydroxychloroquine [HCQ], leflunomide [LEF]) will be allowed but are not required.

There will be a screening phase of approximately 6 weeks, a treatment phase of approximately 2 years that will include a double-blind placebo-controlled period from Week 0 to Week 24 and an active controlled treatment phase from Week 24 to Week 100, and a safety follow-up at Week 112 (approximately 12 weeks after the last intended dose at Week 100 per protocol).

An overview of the study design is provided in Figure 1.

medications up to the maximum allowed dose, as selected by the investigator.

At Week 0, participants who satisfy all inclusion and exclusion criteria will be randomly assigned to 1 of the following 3 treatment groups in a 1:1:1 ratio using permuted block randomization stratified by baseline non-biologic DMARD use (yes/no).

- Group I (n=150), guselkumab 100 mg SC every 8 weeks (q8w): Participants will receive SC guselkumab 100 mg at Weeks 0, 4 then q8 at Weeks 12, 20, 28, 36, 44, 52, 60, 68, 76, 84, 92, and 100. Participants will receive placebo SC at Weeks 8, 16, 24, 32, 40, 48, 56, 64, 72, 80, 88, and 96 to maintain the blind.
- Group II (n = 150), guselkumab 100 mg SC every 4 weeks (q4w): Participants will receive SC guselkumab 100 mg at Weeks 0, 4, then q4 at Weeks 8, 12, 16, 20, 24, 28, 32, 36, 40, 44 48, 52, 56, 60, 64, 68, 72, 76, 80, 84, 88, 92, 96, and 100.
- Group III (n=150), placebo and placebo cross-over: Participants will receive SC placebo at Weeks 0, 4, 8, 12, 16 and 20, and will cross over at Week 24 to receive SC guselkumab

3

[†] The first DBL will occur when all randomized participants have either completed the Week 24 assessments or terminated study participation prior to the Week 24 visit.

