5.5. Other Analyses

5.5.1. Pharmacokinetics

PK analyses will be performed on the PK analysis set, defined as participants who have received at least 1 complete dose of guselkumab and have at least 1 valid blood sample drawn for PK analysis (Section 4.6). Subjects will be analyzed according to the treatment groups that they actually receive. No imputation for missing concentration data will be performed.

Descriptive statistics (N, mean, SD, median, range, CV (%) and IQ range) will be used to summarize serum guselkumab concentrations at each sampling time point by treatment group. PK data may be displayed graphically. The following analyses will be performed by treatment group as appropriate:

- Summary of serum guselkumab concentrations at each visit by treatment group
- Proportion of subjects without detectable serum guselkumab concentration at each visit by treatment group
- Summary of serum guselkumab concentrations at each visit by treatment group and body weight
- Summary of serum guselkumab concentrations at each visit by treatment group and baseline MTX use (Yes, No)
- Summary of serum guselkumab concentrations by baseline CRP levels
- Plot of median (IQ) serum guselkumab concentrations over time by treatment group

In addition, the relationship between serum guselkumab concentrations and safety or efficacy may be explored.

For summary statistics of serum guselkumab concentrations, concentration values below the LLOQ will be treated as zero. Once a subject meets one of the following dosing deviation criteria, the subject's data will be excluded from the by-visit data analyses from that point onwards.

Dosing deviation criteria:

- Discontinue SC guselkumab administrations.
- Skipped an SC guselkumab administration.
- Received an incomplete/ incorrect SC dose.
- Received an incorrect SC study agent.
- Received an additional SC guselkumab dose.

In addition, if a subject has an administration outside of visit windows (Section 5.1.1), the concentration data collected at and after that visit will be excluded from the by-visit data analyses. Additional exclusions for incongruous PK data to be implemented based on Janssen SOP-07952.

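### The by-visit PK exclusion for out-of-window injections is not limited to guselkumab, so as written a mistimed placebo injection removes later concentrations that it cannot affect

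*SAP*

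**What the plan says.** SAP Section 5.1.1.1 sets the windows: "All post-baseline visits from baseline through Week 24 will have a visit window of ± 4 days", then ±7 days from Week 28 through Week 100 and ±14 days for the final safety visit. It states their purpose: "This information will be used to identify out-of-window dosing or visits". For PK it adds that "if a participant has an administration outside the visit window at a visit, the concentration data collected at and after that visit will be excluded". The scope is given in the words that follow: the data "will be excluded from the by-visit data analyses".

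SAP Section 5.5.1 repeats the rule: "if a subject has an administration outside of visit windows (Section 5.1.1), the concentration data collected at and after that visit will be excluded". Just before it stand five dosing-deviation criteria that also end a participant's contribution to the by-visit analyses. Three name guselkumab: discontinuing it, "Skipped an SC guselkumab administration" and "Received an additional SC guselkumab dose". The other two (an incomplete or incorrect dose, and an incorrect study agent) do not.

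SAP Section 1.2 gives the injection schedule. In Group I, "Participants will receive placebo SC at Weeks 8, 16, 24, 32" and at further eight-week steps to Week 96. Group III receives only placebo from Week 0 to Week 20 and starts guselkumab at Week 24.

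**The concern.** A placebo injection has no effect on serum guselkumab, whenever it is given. The window rule nevertheless turns on any administration. Followed literally, it removes by-visit concentrations from participants whose guselkumab doses were all on time.

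It also conflicts with the criteria beside it. A Group I participant who omits the Week 8 placebo keeps all by-visit data. One who receives that placebo five days late loses everything from Week 8 on. There is no pharmacokinetic reason for that ordering.

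Serum guselkumab concentration over time is a stated secondary endpoint, and higher exposure is part of the protocol's rationale for studying q4w (Protocol Sections 4.2 and 4.3). In Group II every trigger is a real deviation in guselkumab timing; in Groups I and III many triggers are not. The by-visit summaries are therefore filtered for different reasons in different groups.

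Triggers are foreseeable. Protocol Section 6.4 generally accepts a dose within about two weeks of the scheduled visit, which is wider than either dosing window. From Week 32 on, all nine remaining Group I placebo injections fall at visits where home dosing is allowed (Schedule of Activities, footnote m); only two Group I guselkumab doses do (Weeks 60 and 92).

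**Working it through.** The plan states no figure to reproduce here. The check is a reading of the text, a count, and an illustration under an assumed rate.

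**Does the text reach placebo?** Neither section names placebo or excludes it. SAP Appendix 3 applies the Section 5.1.1.1 windows to study intervention administrations, and Protocol Section 2 defines study intervention as guselkumab or placebo. In the documents' own terms, the literal reading includes placebo.

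**Injections (SAP Section 1.2).**
- Every group has 26 injections, Weeks 0 to 100 every 4 weeks; 25 are after baseline and carry a window.
- Group I: 14 guselkumab (13 after Week 0) and 12 placebo; 14 + 12 = 26.
- Group II: 26 guselkumab (25 after Week 0).
- Group III: 6 placebo (5 after Week 0) and 20 guselkumab; 6 + 20 = 26.

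**PK samples (Protocol Section 1.3).** Weeks 0, 4, 8, 12, 16, 20, 24, 36, 44, 52, 76, 100 and 112: 13 samples, taken before dosing at dosing visits.

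**Samples removed by one out-of-window placebo injection.**
- Group I, Week 8: samples at Weeks 8 to 112, 11 of 13.
- Group I, Week 16: 9 of 13. Week 24: 7 of 13.
- Group III, any of Weeks 4 to 20: all six samples after guselkumab starts (Weeks 36, 44, 52, 76, 100, 112). The Week 24 sample precedes the first guselkumab dose.
- Either group, placebo skipped: none under the listed criteria.

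**Share of participants excluded by Week 100.** Let p be the chance that an injection is out of window, assumed equal and independent across injections. The documents give no value for p, so a range is shown.
- Rule as written: 1 − (1 − p)^25 in every group.
- Limited to guselkumab: 1 − (1 − p)^13 in Group I; 1 − (1 − p)^20 in Group III; unchanged in Group II.

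| Assumed p | As written, all groups | Group I, guselkumab only | Group III, guselkumab only |
|---|---|---|---|
| 1% | 22.2% | 12.2% | 18.2% |
| 2% | 39.7% | 23.1% | 33.2% |
| 5% | 72.3% | 48.7% | 64.2% |

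The net excess in Group I is 39.7 − 23.1 = 16.6 points at 2% and 72.3 − 48.7 = 23.6 points at 5%.

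Under equal p the rule as written excludes the same share in every group. The groups differ in why participants are excluded, not in the expected rate.

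**The case against.** The best defence is that the authors meant guselkumab only. The sentence sits in a guselkumab PK section and is introduced as an addition to criteria that mostly name guselkumab. Appendix 3 concerns protocol deviations, not PK exclusions, and Section 5.5.1 refers further exclusions to a company procedure not available here. That is plausible, and the SAP never says that placebo counts. But the words on the page include it, and two programmers could produce different tables from them.

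The second objection is about sample timing, and it stands. If the whole visit is late, the pre-dose sample is late too. A Group I Week 8 visit held 10 days late gives a concentration 38 days after an on-time Week 4 dose instead of 28. Removing that one sample is right. Merely adding the word guselkumab would leave such samples in the summaries at placebo visits, and Group I has placebo and PK sampling together at Weeks 8, 16 and 24. This justifies removing the off-time sample, not every later one.

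A reader might infer three stronger conclusions that the documents do not support:
- That the concentrations are discarded altogether. The sentence covers by-visit analyses only. PK analysis set membership (SAP Section 4.6) is unchanged, and population PK modelling has its own plan (Protocol Section 9.4.5).
- That the chance of at least one placebo trigger, 1 − (1 − p)^12, is the loss due to the flaw. In Group I by Week 100 it is 21.5% at 2% and 46.0% at 5%, but it counts participants whom a guselkumab trigger would exclude anyway. The net figures are 16.6 and 23.6 points.
- That trial conclusions are at risk. The PK endpoint is descriptive, and none of the 22 hypotheses in SAP Appendix 10 concerns it.

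**Conclusion.** The point holds for the by-visit PK summaries. As written, the rule lets a mistimed placebo injection remove later concentrations that it cannot affect: 11 of 13 scheduled samples for a Week 8 trigger in Group I, and all six samples after guselkumab starts for a Week 4 to 20 trigger in Group III. These counts come straight from the schedules and need no assumption beyond the literal reading.

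How many participants would be affected cannot be settled from the documents. The percentages rest on an assumed rate, on independence, and on one rate for both the ±4-day and ±7-day windows. Lateness probably clusters within participants, which at the same average rate would lower the share affected.

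It is worth correcting because it concerns a stated secondary endpoint and the remedy is cheap. Efficacy, safety and multiplicity control are untouched.

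**What to change.** Make two changes, worded identically in SAP Sections 5.1.1.1 and 5.5.1.

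1. Trigger the rule only on a guselkumab administration outside the visit window, and exclude from the by-visit analyses the concentrations collected after that administration. Because samples are pre-dose, the sample of the triggering visit is then judged by its own timing.
2. Add a separate sample-time rule: an individual sample drawn outside its visit window is left out of the by-visit summary for that visit only, at guselkumab and placebo visits alike.

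The cost is a short SAP revision and a small amount of extra programming with actual treatment and sample dates. No new data are needed: sample dates are already recorded, and some Sponsor personnel are unblinded for analysis from the Week 24 lock. Under equal p, Group II would then lose a larger share of participants than Group I, because it has more guselkumab injections, but every exclusion under the first rule would reflect a real guselkumab timing deviation.

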5.1.2. Pooling Algorithm for Analysis

Data from all investigational centers/sites will be pooled for analyses.

5.2. Participant Dispositions

The number of participants screened, randomized and treated will be summarized by geographic region, country, and investigational site.

The number of participants in the following disposition categories will be summarized throughout the study by intervention group and overall.

- Participants who received study intervention
- Participants who completed the study
- Participants who discontinued study intervention
- Reasons for discontinuation of study intervention
- Participants who terminated study prematurely
- Reasons for termination of study

Listings of participants will be provided for the following categories:

- Participants who discontinued study intervention
- Participants who terminated study prematurely
- Participants who were unblinded prior to the Week 112 DBL
- Participants who were randomized yet did not receive study intervention
- Summaries of participant demographic and baseline characteristics are in Section 6.2 (Appendix 2).

5.2.1. Intercurrent Events (ICEs) and Early Escape (EE)

Tabulations by randomized intervention group will be provided for participants who met EE criteria at Week 16 and for participants who met 1 or more ICEs for the Adjusted Composite Estimand prior to Week 24 defined in Section 5.3.4.2.1.

In addition, participants who met any ICE criteria will be presented in data listings.

5.3. Efficacy Analyses

5.3.1. General Method of Analysis

In general, descriptive statistics, such as mean, standard deviation (SD), median, interquartile (IQ) range, minimum, and maximum for continuous variables, and counts and percentages for discrete variables will be used to summarize most data.

Statistical comparison between a guselkumab group (100mg q4w or 100mg at Weeks 0, 4 and then q8w) and the placebo group will be performed by visit through Week 24. No treatment comparisons will be performed after Week 24.

Binary Response Efficacy Endpoints

For binary response efficacy endpoints where any portion of the missing data is imputed using Multiple Imputation (MI) (see Section 6.12 for technical details), treatment comparisons will be performed using a Cochran-Mantel-Haenszel (CMH) stratified by baseline use of non-biologic DMARDs (yes, no) on each of the imputation sets, and the inferences from the analysis of each imputed data are pooled. The within imputation variance and between imputation variance are combined to estimate the total variance of the stratum adjusted difference of proportions. This estimate of the variance and critical values from the t-distribution are used to calculate the confidence interval for the stratum adjusted difference of proportions. The SAS procedure PROC MIANALYZE is used where the critical value is based on the t-distribution which is different from the analysis not based on MI where normal distribution is used. The large number of observations in our data imply that the critical values from the t-distribution are almost identical to the critical values from the standard normal distribution. The Wilson-Hilferty (Ratitch 2013) transformation is used to pool the CMH statistics from each imputed data set to calculate the p-value.

For analyses where all missing data is imputed only a single time (eg, non-responder imputation for all missings) or not imputed with the missing assumed Missing Completely at Random (MCAR), treatment comparisons will generally be performed using a CMH test stratified by baseline use of non-biologic DMARDs (Yes/No). The magnitude of the treatment difference will be estimated by the difference in response rates between the guselkumab and placebo groups with a 95% confidence interval (CI) calculated based on Wald statistics (Kim 2013). The Mantel Fleiss criterion will be used to determine the appropriateness of using the CMH test. If the Mantel Fleiss criterion is not satisfied, the Fisher's exact test will be used instead of the CMH test to compare the two intervention groups.

For endpoints where any portion of the missing data is not imputed, but still needs to be accounted for under Missing at Random (MAR) assumptions, the **Generalized Linear Mixed Model** (GLMM) will be used (for more details see Appendix 13 in Section 6.13).

For subgroup analyses, a **logistic regression model** using data from all 3 intervention groups will be used to obtain odds ratios and associated 95% CI. If any missing data were multiply imputed, the logistic regression model will be run on each of the imputation sets, and the odds ratios from each imputation set will have the log transformation applied before pooling across imputation sets.

Once combined, the log transformed odds ratio and 95% CI will be back transformed to their original scale (Ratitch 2013) and presented. The treatment*subgroup interaction p-value will be obtained separately, based on logistic regression on the observed data and with only the data from the 2 intervention groups currently being analyzed fed into the model.

Continuous Efficacy Endpoints

For most continuous endpoints where any portion of the missing data is imputed using MI (see Appendix 12 in Section 6.12 for technical details), treatment comparisons will be performed using an Analysis of Covariance (ANCOVA) model based on each of the imputation sets. The estimate of the mean change from baseline is the average of the mean change taken over all the MI data sets. The estimate of the variance of the mean change from baseline is the weighted sum of the average within-imputation variance and the between-imputation variance. The CI for the mean change from baseline uses critical values from the t-distribution. The treatment difference between each guselkumab group versus the placebo group will be tested for each imputation dataset and then the analysis results across all imputation datasets will be combined. The treatment difference in the change from baseline is estimated by the average of the treatment differences over the MI data sets. The estimate of the variance of the treatment difference in the change from baseline is the weighted sum of the average within-imputation variance and the between-imputation variance, under the assumption of homogeneity of variance between intervention groups for performing ANCOVA within each imputation dataset. The CI is based on the critical values from the t-distribution. The large number of observations in our data imply that the critical values from the t-distribution are almost identical to the critical values from the standard normal distribution.

The ANCOVA model will be based on the original scale and will include intervention group, baseline score, and baseline use of non-biologic DMARDs (yes, no) as the explanatory factors. The model will include data from all the 3 intervention groups.

For analyses where all missing data is imputed only a single time (eg, change=0 for all missings) or not imputed with the missing assumed MCAR, treatment comparisons will generally be performed using ANCOVA.

For endpoints where any portion of the missing data is not imputed, but still needs to be accounted for under MAR assumptions, the **Mixed-Effect Model Repeated Measures (MMRM)** model will be used (for more details see Appendix 13 in Section 6.13).

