- 5. (Supplementary Analysis 1) To support regulatory decision making, the Treatment Policy Estimand (Section 5.3.4.2) will also be evaluated as a supplementary analysis. In this analysis, the observed ACR 20 response for all participants will be used regardless of whether or not ICE criteria are met prior to Week 24, and the missing ACR 20 response will be imputed by FCS MI (Section 5.3.2.1) on the component level under the assumption that data are MAR. Treatment comparisons for each imputation data set will be based on a CMH test stratified by baseline use of non-biologic DMARDs (yes, no), as per Section 5.3.1. This analysis will be conducted based on the FAS-UKR analysis set.
- 6. (Supplementary Analysis 2) An additional tipping point analysis for the Treatment Policy Estimand will be performed. The observed ACR 20 response for participants will be used regardless of whether or not ICE criteria are met prior to Week 24, and the missing ACR 20 response will be imputed by FCS MI (Section 5.3.2.1) on the component level under the assumption that data are MAR. In this analysis, a pair of deltas will be added to the predicted response rates from MI method depending on guselkumab or placebo group to new MI datasets (Section 5.3.2) to evaluate deviation from the assumption of MAR for missing data. The same analysis method as in the primary analysis will be applied for the pairs of deltas. The analysis will be done for pairs of delta values include the scenarios where participants on

guselkumab have worse outcomes than participants on placebo. This analysis will be conducted based on the FAS-UKR analysis set.

Subgroup Analyses

Subgroup analyses will be performed using the Adjusted Composite Estimand using a logistic regression model on the multiply imputed data to evaluate treatment consistency in proportion of participants who achieve an ACR 20 response at Week 24 over baseline demographics, baseline disease characteristics, and prior and baseline medication use. A forest plot will be produced for all subgroups listed in Section 5.5.5. The odds ratios and the corresponding 95% CIs will also be provided for each of the subgroups (Section 5.3.1). In addition, the p-values for interaction of the intervention groups and the subgroups will also be provided when a subgroup has at least 2 categories.

If the number of participants in a subgroup is too small (eg, <10), subgroups may be pooled for analyses.

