Subgroup Analyses (based on Adjusted Composite Estimand) – FAS subgroups	ICEs 1-3 considered as TF ICEs 4 and 5, data not used, but rather imputed using FCS MI Missing data due to Natural Disaster or Major Disruption assumed MAR, imputed via FCS MI Missing data not due to Natural Disaster or Major Disruption assumed MAR but conservatively imputed as non-response	 Odds ratio and 95% CI for treatment comparison P-value from logistic regression for the interaction of intervention group and subgroup variable Graphical: forest plots

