5.5.5. Definition of Subgroups

To evaluate the consistency in the primary efficacy endpoint (proportion of participants who achieve ACR 20 at Week 24) and the major secondary endpoint over demographics, baseline characteristics, prior and baseline medication use, subgroup analyses will be performed. The subgroups include, but are not limited to, the following:

Subgroup	Variant	Definition
Demographics		
Gender		• Male
		Female
Race		• White
A 1 1' ()		• Other • <45
Age at baseline (year)		• <45 • ≥45 and <65
		• ≥65
Body weight at baseline (kg)	1 (Categories)	• ≤90
, ,		• >90
Body weight at baseline (kg)	2 (Quartiles)	• 1st Quartile: ([##] to [##])
		• 2nd Quartile: ([##] to [##])
		• 3rd Quartile: ([##] to [##])
Body mass index at baseline		4th Quartile: ([##] to [##])Normal [<25]
(kg/m ²)		• Overweight [≥25 to <30]
(kg/m ⁻)		• Obese [≥30]
Participating regions		Eastern Europe (except Russia, Ukraine, Poland)
		North America
		• Poland
		• Russia
		 Ukraine Other countries
		• Other countries
Baseline disease characteristics	5	
PsA duration at baseline (year)		• <1
		• ≥1 to <3
PsA subtype		• ≥3 • distal interphalangeal joint involvement
1 sA subtype		polyarticular arthritis with absence of rheumatoid
		nodules
		asymmetric peripheral arthritis
		spondylitis with peripheral arthritis
Number of swollen joints at		• <10
baseline		• 10 to 15 • >15
Number of tender joints at		• <10
baseline		• 10 to 15
		• >15
HAQ-DI score at baseline		• <1
		• 1 to 2
CDD (1 1' (/IT)	1.(0.4	• >2
CRP at baseline (mg/dL)	1 (Categories)	• <1 • 1-2
		• 1-2 • ≥2
CRP at baseline (mg/dL)	2 (Quartiles)	• 1st Quartile: ([##] to [##])
··· - ··· · · · · · · · · · · · · · · ·	(((• 2nd Quartile: ([##] to [##])
		• 3rd Quartile: ([##] to [##])
		• 4th Quartile: ([##] to [##])
Dactylitis at baseline		• Yes
Enthesitis at baseline		• No
Enthesitis at baseline		YesNo
	1	- 140

Subgroup	Variant	Definition
7.07		
PASI score at baseline		• <12
		• ≥ 12 to ≤ 20
		• ≥20
BSA of psoriasis at baseline		• <3%
		• $\geq 3\%$ to $< 10\%$
		• $\geq 10\%$ to $< 20\%$
		• ≥20%
IGA score at baseline		• <2
		• ≥2
Prior and baseline medication	use	
Reason for discontinuation for		 Efficacy - inadequate response (IR)
prior anti-TNF		Safety - contraindication or intolerance (but not IR)
		• Other
Use of non-biologic DMARDs		• Yes
(MTX, SSZ, HCQ, LEF) at		• No
baseline (based on eCRF)		
Oral corticosteroids at baseline		• Yes
(based on eCRF)		• No
NSAIDs at baseline		• Yes
		• No

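### The subgroup interaction p-value is computed on undefined observed data, while the odds ratios beside it are multiply imputed and Table 6 places both under the Adjusted Composite Estimand

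*SAP*

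**What the plan says.** SAP 5.3.1 sets two rules for subgroup analyses of binary endpoints. For the estimates, a logistic model "using data from all 3 intervention groups will be used to obtain odds ratios and associated 95% CI", and where values are multiply imputed "the logistic regression model will be run on each of the imputation sets" and the log odds ratios are pooled. For the interaction, "The treatment*subgroup interaction p-value will be obtained separately, based on logistic regression on the observed data", "with only the data from the 2 intervention groups currently being analyzed fed into the model".

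The primary-endpoint section makes no such split. SAP 5.3.4.4 states that "Subgroup analyses will be performed using the Adjusted Composite Estimand using a logistic regression model on the multiply imputed data", and the same paragraph adds that "the p-values for interaction of the intervention groups and the subgroups will also be provided when a subgroup has at least 2 categories". The subgroup row of Table 6 (SAP 5.3.4.5) lists "P-value from logistic regression for the interaction of intervention group and subgroup variable" against these data rules: ICE 1-3 as treatment failure; multiple imputation for ICE 4/5 and for data missing through disruption; non-response for other missing data. Neither place mentions an observed-data exception.

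SAP 5.5.5 includes "Participating regions" among the subgroups, with Ukraine, Russia and Poland as separate levels.

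**The concern.** A reader of a forest plot expects the interaction p-value to test the differences between the plotted odds ratios. Under SAP 5.3.1 it comes from another data set, and the SAP does not say which. A programmer following Table 6 and one following SAP 5.3.1 would report different p-values for the same analysis.

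At stake is how the consistency of the primary effect is described. Under this estimand, multiple imputation arises only from the disruption involving Ukraine and neighbouring countries or from COVID-19 restrictions. The participants affected may therefore be unevenly spread over the region levels.

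**Working it through.** **1. Stated figures.** The SAP gives no number for this point. The planning rates used below reproduce its power claim of more than 99% (150 per arm, two-sided 0.05, pooled normal approximation): 0.9998 for 22% v 52%, above 0.9999 for 22% v 59%, and 0.9965 for 19.8% v 44.4%.

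**2. What observed data could mean.** Elsewhere in the SAP the term means values used whatever ICEs occurred (5.3.4.2.2) or analysis without imputation (notes to Table 8). That is reading A. B and C are narrower.

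| Participant at Week 24 | Odds ratios | A: ICEs ignored, nothing imputed | B: ICE rules kept, missing dropped | C: only multiply imputed values removed |
|---|---|---|---|---|
| ICE 1-3 | non-responder | recorded value, or dropped | non-responder | non-responder |
| Missing, not disruption | non-responder | dropped | dropped | non-responder |
| ICE 4/5, value recorded | multiply imputed | recorded value | dropped | dropped |
| Missing through disruption | multiply imputed | dropped | dropped | dropped |

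The last two rows differ from the odds-ratio column on every reading. Row 2 differs on A and B, and row 1 on A.

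**3. Effect on the ratio of odds ratios.** Inputs are the PSA3001 rates (placebo 22.2%, q4w 59.4%), with ICE 1-3 and missing rates assumed and independent of response. With ICE rate i and missing rate m, the response rate under the composite and non-responder rules is p(1-i)(1-m). Take ICE rates of 10% (placebo) and 5% (q4w) in both subgroup levels, and m = 2% in one level and 10% in the other:

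- m = 2%: q4w 0.594 × 0.95 × 0.98 = 0.553; placebo 0.222 × 0.90 × 0.98 = 0.196; odds ratio 5.08.
- m = 10%: q4w 0.508; placebo 0.180; odds ratio 4.71.
- Ratio 4.71/5.08 = 0.93. In the recorded responses it is 1.00.

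Raising m to 30% in the second level gives 0.79. Placebo ICE of 20% with m = 10% there gives 1.07. ICE rates of 30% and 10% with m = 20% give 1.04. The plotted odds ratios can therefore differ between levels where recorded responses do not, and the reverse can also happen.

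**4. Effect on the p-value.** There were 500 simulated trials at planning rates of 22% (placebo) and 59.4% (q4w), with 150 per arm and no interaction in recorded responses. A quarter of participants were in the second level. Missing rates were 3% v 10% and placebo ICE rates 10% v 15%, halved in active arms. The test kept on average 286 of 300 participants. Against the composite/non-responder p-value:

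| Reading | Median absolute change in p | Other side of 0.10 |
|---|---|---|
| A | 0.14 | 6.6% |
| B | 0.07 | 2.8% |

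These runs contain no multiple imputation, so they size the loss of the failure and non-responder rules. Reading C was not simulated.

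**5. Two arms or three.** In one simulated data set the q4w-placebo interaction had p = 0.1412 in both models without covariates. With DMARD use as covariate it was 0.1417 (three arms) and 0.1419 (two arms).

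**6. Cost of pooling.** The ACR imputation model (SAP Appendix 12) contains the ACR components, intervention group and DMARD use, but no subgroup term. Assume a region with 20% of participants, 40% of them imputed, and 22% response in both arms. Elsewhere assume 22% v 59%, fully observed. Ignore earlier-visit data, which makes this an upper bound.

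- Active rate the imputation draws on: (0.12 × 0.22 + 0.80 × 0.59)/0.92 = 0.542.
- Region's active rate after imputation: 0.6 × 0.22 + 0.4 × 0.542 = 0.349.
- Region's odds ratio: (0.349/0.651)/(0.22/0.78) = 1.90, against a true 1.0.
- Elsewhere the odds ratio is 5.10. The log interaction falls from 1.63 to 1.63 - 0.64 = 0.99, or by 39%.

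**The case against.** The strongest defence is that the separate fit looks deliberate and may be the safer test. Step 6 shows that imputing without subgroup terms can hide a real interaction. If outcomes are missing at random given arm and subgroup, a logistic fit without the imputed values avoids this. That stands as a drawback of pooling. But it applies equally to the odds ratios already planned, the SAP gives no such reason, and it does not explain dropping the ICE 1-3 and non-responder rules.

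The p-value also carries limited weight. SAP 5.3.4.4 offers it in addition to the forest plot and odds ratios, the protocol (9.4.2) provides interaction tests only if appropriate, no threshold is attached, and it lies outside the testing sequence. Sensitivity Analysis 2 repeats the primary analysis without Ukraine. All of this stands and limits the consequence.

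Three stronger readings are tempting, and the documents do not support them:

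- *That using two arms rather than three distorts the test.* Step 5 shows almost no effect on a pairwise contrast.
- *That the test certainly targets another estimand and also drops the ICE 4/5 participants.* These need different readings. On A the estimand changes, but ICE 4/5 participants with recorded values stay in. On C they are dropped, but the estimand can be the same.
- *That the region test is the most distorted.* No share of imputed outcomes is given by country. SAP 4.2 says that no site had every participant without Week 24 primary data or with two or more missed doses, and SAP 4.3 describes Ukrainian sites as potentially affected.

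**Conclusion.** The conflict is real: SAP 5.3.1 sets a data rule for the interaction p-value that does not match SAP 5.3.4.4 or Table 6, and its key term is undefined. On every reading the test and the odds ratios treat multiply imputed outcomes differently. On the SAP's usual meaning the ICE 1-3 and non-responder rules are lost too, so the p-value may not test what the forest plot shows.

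The likely effect is modest. The sizes in steps 3 and 4 rest on assumed ICE and missing rates and on independence of ICEs from response. Uneven impact across region levels is possible, since Ukraine is its own level, but cannot be quantified from the documents. The change should be made for a consistent supportive analysis; the primary result is unaffected.

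**What to change.** In SAP 5.3.1, replace the observed-data wording with a rule that:

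- applies the Adjusted Composite handling: ICE 1-3 and missing data not due to disruption as non-response, multiple imputation for ICE 4/5 and disruption-related missing data;
- fits the treatment-by-subgroup model in each of the 200 imputation sets of Appendix 12;
- pools the interaction terms by Rubin's rules, with a multivariate Wald test where there is more than one degree of freedom (region has six levels, so five in a two-arm model).

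The two-arm model may stay.

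To cover the pull toward no interaction, either keep as a sensitivity check the fit without multiply imputed values, with the ICE 1-3 and non-responder rules still applied, or, for region, add the subgroup and its treatment interaction to the imputation model.

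The pooled test with the sensitivity check needs a short SAP edit and no new imputation. Changing the imputation model for region would need a further imputation run.
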